2.1 Design overview

This efficacy trial adopts a two-arm, two-level design with pupils clustered into schools. The unit of randomisation is the school. All pupils in Year 8 in the participating schools undertake baseline tests from November 2023 to January 2024 and outcome tests at the follow-up stage in March 2025. The schools within the control group continue to function according to business-as-usual. There is no waitlist design in this trial.

The randomisation process adopts the minimisation approach considering whether the percentage of students eligible for free school meals (FSM6) at each school fell above or below the median percentage of FSM6 across all schools in the sample. More detail is discussed in the next section.

The randomisation process was executed by colleagues from the University of Kent, operating independently from the evaluation team at Ipsos UK. The University of Kent was provided with a list of schools without school names but marked with ID codes, ensuring they could not discern the schools' identities, thus maintaining blindness during the randomisation procedure. The randomisation procedure occurred in two phases: one in early December 2023 and another in January 2024. Initially, the intention was to conduct baseline testing for

all schools in November and proceed with randomisation in December. However, extending the timeline became imperative to accommodate additional time for recruitment, data collection, fieldwork, and the constraints posed by the Christmas break and Ofsted inspections, allowing schools ample opportunity to implement the surveys.

The primary outcome is externalising behaviour at pupil level in Year 8 measured by the Strengths and Difficulties Questionnaires (SDQ) – Combined Conduct and Hyperactivity Scale. There is a baseline measurement before the start of the intervention and then a follow-up measurement once the intervention ends, namely, 15 months after randomisation. The secondary outcomes at pupil levels in Year 8 consist of internalising behaviour, prosocial behaviours, total difficulties, non-psychotic psychological distress, well-being, sense of connectedness, exclusions and suspensions, and school attendance. Other secondary outcomes at the school staff level are attitudes related to TIC, school staff's well-being, school staff retention and sickness. Finally, the % of exclusions, suspensions and attendance of CYP at the school level will be collected. Detailed instruments for each outcome are described in Table 1 below.

Table 1 Summary of trial design

Trial design		Two-arm and cluster randomised at the school level
Unit of randomisation		School
Stratification variables (if applicable)		Binary indicator of school-level percentage of pupils eligible for Free School Meals (Below median percentage vs. At or above median percentage)
Primary outcome	variable	(CYP) Externalising behaviour
	measure (instrument, scale, source)	SDQ – Combined conduct and hyperactivity scale scores (0-20) (Survey)
Secondary outcome(s)	variable(s)	(CYP) Internalising behaviour
		(CYP) Prosocial behaviour
		(CYP) Total difficulties
		(CYP) Non-psychotic psychological distress

		
(CYP) Well-being
 
(CYP) Sense of connectedness
 
(CYP) Exclusions & suspensions
 
(CYP) School attendance
 
(School staff) Attitudes related to TIC
 
(School staff) Well-being
 
(School) Staff retention
 
(School) Staff sickness
 
(School) Exclusions & suspensions of CYP
 
(School) School attendance of CYP

	
measure(s) (instrument, scale, source)
	
(CYP) Internalising behaviour: SDQ – Combination of emotional regulation and peer problems (0-20) (Survey)
 
(CYP) Prosocial behaviour: SDQ – sub-dimension of prosocial behaviour (0-10) (Survey)
 
(CYP) Total difficulties: SDQ – Combination of sub-dimensions of conduct, hyperactivity, emotional regulation, and peer problems (0-20) (Survey)
 
(CYP) Non-psychotic psychological distress: General Health Questionnaire (GHQ12) (0-12) (Survey)
 
(CYP) Well-being: Short Warwick Edinburgh Mental Well-being Scale (7-35) (Survey)
 
(CYP) Sense of connectedness: School Connectedness Scale (Survey)
 
(CYP) Exclusions & suspensions: administrative records
 
(CYP) School attendance: administrative records
 
(School staff) Attitudes related to TIC: Attitudes Related to Trauma Informed Care (ARTIC) (Survey)
 
(School staff) Well-being: Short Warwick Edinburgh Mental Well-being Scale (7-35) (Survey)
 
(School) staff retention: administrative records

		
(School) staff sickness: administrative records
 
(School) Percentage of exclusions & suspensions of CYP: administrative records
 
(School) Percentage of school attendance of CYP: administrative records

Baseline for primary outcome	variable	(CYP) Externalising behaviour
	measure (instrument, scale, source)	SDQ – Combined conduct and hyperactivity scale scores (Survey)
Baseline for secondary outcome	variable	
(CYP) Internalising behaviour
 
(CYP) Prosocial behaviour
 
(CYP) Total difficulties
 
(CYP) Non-psychotic psychological distress
 
(CYP) Well-being (CYP) Sense of connectedness
 
(CYP) Exclusions & suspensions
 
(CYP) School attendance
 
(School staff) Attitudes related to TIC
 
(School staff) Well-being
 
(School) Staff retention
 
(School) Staff sickness
 
(School) Percentage of exclusions & suspensions of CYP
 
(School) Percentage of school attendance of CYP

	measure (instrument, scale, source)	
(CYP) Internalising behaviour: SDQ – Combination of emotional regulation and peer problems (0-20) (Survey)
 
(CYP) Prosocial behaviour: SDQ – sub-dimension of prosocial behaviour (0-10) (Survey)
 
(CYP) Total difficulties: SDQ – Combination of sub-dimensions of conduct, hyperactivity, emotional regulation, and peer problems (0-20) (Survey)

		
(CYP) Non-psychotic psychological distress: General Health Questionnaire (GHQ12) (Survey)
 
(CYP) Well-being: Short Warwick Edinburgh Mental Well-being Scale (Survey)
 
(CYP) Sense of connectedness: School Connectedness Scale (Survey)
 
(CYP) Exclusions & suspensions: administrative records
 
(CYP) School attendance: administrative records
 
(School staff) Attitudes related to TIC: Attitudes Related to Trauma Informed Care (ARTIC) (Survey)
 
(School staff) Well-being: Short Warwick Edinburgh Mental Well-being Scale (Survey)
 
(School) staff retention: administrative records
 
(School) staff sickness: administrative records
 
(School) Number of exclusions & suspensions of CYP: administrative records
 
(School) School attendance of CYP: administrative records

--	--	---

2.2 Sample size calculations overview

Table 4 describes the minimum detectable effect size (MDES) estimates and sample sizes for the TISUK impact evaluation. The goal was to adopt conservative assumptions to allow for a well powered statistical analysis sufficient to detect an MDES below 0.20¹ and sub-population analysis.

Sample size estimations and assumptions

The goal is to calculate the required sample size for detecting a meaningful difference in the primary outcome measure of adolescent externalising behaviours. Key parameters involved in the calculation include the effect size, power, alpha level, and accounting for the clustered

¹ All YEF evaluations require a minimum detectable effect (MDES) below 0.20

design. Table 4 describes the sample size calculated using Stata 17© according to the following assumptions:

1. A pre-post zero correlation is assumed for externalising behaviours, as there are no reliable sources from which to base an estimate. Furthermore this represents the most conservative scenario for sample size estimation. Assuming a non-zero correlation would risk underestimating the required sample size if the assumed correlation is too high, we obtain a conservative sample size estimate for a covariance analysis by omitting this parameter and assuming a zero correlation. .
2. The SDQ (externalising scale) adolescent population mean is 6.0, and the assumed pooled Standard Deviation (SD) is 1.74², using the UK self-report population norms for 11-15 year olds³. Thus, to detect an effect size of 0.2 or greater, we need an SDQ externalising behaviours score difference of 6.0 (control) versus 5.66 (intervention). This difference requires 527 participants in each group, 1,054 for the whole sample.
3. Assuming 10% pupil-level attrition between baseline and follow-up requires a total sample size of 1,172.

Sample Size Calculation

We estimate a required total sample size of 6,798 participants for the proposed cluster randomised controlled trial. This calculation accounts for clustering using the design effect, based on an assumed ICC of 0.03 and a harmonic mean year group size of 200 pupils — assuming an 80% consent rate from the average year group size of 197 in England (ONS, 2023). The design effect is estimated to be 5.8⁴, which inflates the initially calculated sample size of 1,172 participants (586 per group for an individually randomised trial) to 6,798. The ICC estimate of 0.03 is based on previous studies by Shackleton, Hale, Bonell, and Viner (2016) and Parker, Nunns, Xiao, Ford, and Ukoumunne (2021), which estimated ICCs for adolescents' health outcomes across secondary school settings in 21 European countries.

² The SD has been estimated as the standardised SD using the same raw data for both scales

³ <https://www.sdqinfo.org/norms/UKNorm1.pdf>

⁴ This is $1 + (0.03 * 160)$

Given assumptions 1 to 3 above, we need a minimum of at least 25 schools in each arm for an efficient cluster trial, that is 50 schools in total. Nevertheless, we propose double the sample size aiming to recruit 100 schools with 50 on each arm. The rationale for this is further discussed below.

Table 2 provides an overview of the numbers available at the primary endpoint for a variety of school retention rates (100%, 90%, 80%, 70%, 60%) and pupil retention rates (100%, 90%, 80%, 70% and 60%) scenarios. In all scenarios the numbers recruited and followed up are sufficient to meet the sample size requirements when we account for the different design effects (i.e., as more pupils drop out, the design effect, which is a function of the cluster size, decreases, hence the overall sample size decreases). Table 3 describes the impact on effect size by number of schools and pupils retained.

Table 2 Impact of different pupil and school retention rates on sample size

		Proportion of pupils retained				
		100%	90%	80%	70%	60%
Number of schools retained	100	16,000	14,400	12,800	11,200	9,600
	90	14,400	12,800	11,200	9,600	8,640
	80	12,800	11,200	9,600	8,640	7,680
	70	11,200	9,600	8,640	7,860	6,720
	60	9,600	8,640	7,860	6,720	5,760

Table 3 Impact of different pupil and school retention rates on MDES

		Proportion of pupils retained				
		100%	90%	80%	70%	60%
Number of schools retained	100	0.1064	0.1074	0.1086	0.1102	0.1122
	90	0.1122	0.1132	0.1145	0.1161	0.1183

	80	0.1190	0.1201	0.1214	0.1232	0.1255
	70	0.1272	0.1284	0.1298	0.1317	0.1341
	60	0.1374	0.1385	0.1402	0.1422	0.1449

Rationale for Targeting 100 Schools

Targeting 100 schools and 16,000 students is justified by several considerations. First, a larger pool of schools increases the likelihood of recruiting a diverse population of school types (e.g., school-level of deprivation, FSM, different socioeconomic backgrounds) and student demographics, enabling robust subgroup analyses and generalizability of findings across various contexts. Second, a large overall sample size enhances statistical power to detect smaller but potentially meaningful intervention effects, minimising the risk of false negatives and providing reliable findings to inform future interventions. Third, the target sample size was selected to ensure sufficient power for the quasi-experimental design (QED) analysis focused on a targeted subgroup of students. Lastly, a larger sample size accommodates the cluster randomised trial design, accounting for potential clustering effects and maintaining adequate power for the primary analysis.

Table 4 displays the minimum detectable effect in the protocol according to the assumed parameters, target sample size, and the respective effect size after randomisation driven by the achieved number of responses on the primary outcome. Thus, while the MDES in the protocol is an estimation from the assumptions, the MDES estimated in the column 'Randomisation' corresponds to the actual achieved sample size at baseline in the primary outcome from the schools that were randomised. As we are adopting an intention-to-treat approach, the estimation includes responses from 4 schools that dropped out after randomisation.⁵ Those four schools that dropped out belong to the intervention group.

⁵ This means that now the number of schools in the trial are 74 with 4 dropping out from the intervention group after randomisation

Table 4 Sample size calculations and effects size

		Protocol	Randomisation
Minimum Detectable Effect Size (MDES)		0.1064	0.094
Pre-test/ post-test correlations	level 1 (participant)	n/a	n/a
	level 2 (cluster)	n/a	n/a
Intracluster correlations (ICCs)	level 1 (participant)	n/a	n/a
	level 2 (cluster)	0.03	0.015
Alpha		0.05	0.05
Power		0.8	0.8
One-sided or two-sided?		Two-sided	Two-sided
Average cluster size		160⁶	166⁷
Number of clusters	intervention	50	40
	control	50	38
	Total	100	78 ⁸

⁶ Average school size in England is 986, average year size is 200 and accounting for a potential 20% not consenting, hence, cluster size 160.

⁷ This is the actual cluster average size

⁸ Although the initial plan was to allocate schools equally to the intervention and control groups at the randomisation stage, the achieved sample showed a slight difference due to attrition during the recruitment

		Protocol	Randomisation
Number of participants	intervention	8,000	6,391
	control	8,000	7,214
	Total	16,000	13,393 ⁹

The MDES calculations were performed using PowerUp! Tool, developed by Dong and Maynard (2013), which incorporates the formula below according to Bloom, Richburg-Hayes, and Black (2007), for the two-level cluster randomised controlled trials:

$$MDES = M_{n-k*-2} \sqrt{\left(\frac{\rho(1 - R_C^2)}{P(1 - P)J}\right) + \left(\frac{(1 - \rho)(1 - R_i^2)}{P(1 - P)Jm}\right)}$$

Employing this formula enables the inclusion of baseline covariates at the cluster (school) level, pupil level, or both. Our analysis strategy intends to use mean-centered baseline scores within the multilevel models at both the pupil and school levels. Incorporating a covariate at both levels - school and pupil - enhances the trial's precision, resulting in a reduced Minimum Detectable Effect Size (MDES) estimate compared to methodologies that employ only one covariate or none.

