3.2 Sample size calculations

Sample size estimation and assumptions

The sample size calculation is designed to detect a difference of 0.2, YEF's expected maximum MDES value for efficacy evaluations. To detect this difference with 80% power, an alpha of 0.05 and a two-sided test, at least 527 CYP in each group are required, totalling 1,054 CYP.

For the PSM, the sample size estimations starts from the assumption of 15 CYP on average per school at baseline, assuming a follow-up rate of 80% to account for attrition and consent. The harmonic mean of CYP per year group receiving more intensive support is estimated to be 15. Using this and an ICC of 0.03, the estimated clustered design effect is 1.45. This inflates our required sample to 1,528. With 100 schools, 15 participants per class provide a sample of 1500. Incorporating the inverse propensity score weights will reduce the size of the overall sample by a conservative estimate of 30%, resulting in a required sample of 1,070.

Table 7 indicates the impact of different group sizes (pupils per cluster) on the number of schools needed in the intervention arm of the PSM analysis. The table shows that with 15 pupils per cluster, data from at least 36 intervention schools are required. At the lower end, with 10 pupils per cluster, data from 48 schools would be required. If the follow-up rate is 80% as anticipated, 12 pupils per school will be available, requiring circa 42 schools in each arm of the study. While the target is to maintain 50 schools in each arm, these conservative estimates should be considered.

At the point where the PSM is conducted, the pre- and post-test correlation for the primary outcome can be estimated and incorporated into the sample size calculation, potentially adjusting the required sample size.

Table 7 Impact of differential cluster size on the proportion of schools retained for the intervention group

Pupils	15	14	13	12	11	10
Base sample	527	527	527	527	527	527
Design effect (DE)	1.45	1.42	1.39	1.36	1.33	1.30
Adjusted sample	764	748	733	717	701	685
Sample adjusted for IPW	535	524	513	502	491	480
Number of intervention schools	36	37	39	42	45	48

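### The raw-score target (6.0 versus 5.66) rests on an SD of 1.74, but the SAP's own baseline SD is about 4.3; and 527 per group is the 90%-power figure, labelled 80%.

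*SAP*

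**What the plan says.** SAP 2.2, assumption 2 (repeated from Protocol 3.5) takes a population mean of 6.0 and a pooled SD of 1.74 from UK self-report norms. The only explanation of the SD is a footnote: "The SD has been estimated as the standardised SD using the same raw data for both scales". The derivation is not shown. The text continues "Thus, to detect an effect size of 0.2 or greater", "we need an SDQ externalising behaviours score difference of 6.0 (control) versus 5.66 (intervention" arm), and then: "This difference requires 527 participants in each group, 1,054 for the whole sample".

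That sentence names no power level. SAP Table 4 gives 0.8, and SAP 3.2 attaches the same figure to it directly: "To detect this difference with 80% power, an alpha of 0.05 and a two-sided test, at least 527 CYP in each group are required". Protocol Appendix 2 does likewise. From 527 the plan goes to 1,054, then 1,172 after attrition, and then: "We estimate a required total sample size of 6,798 participants for the proposed cluster randomised controlled trial".

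The outcome is described in SAP Table 1 as "SDQ – Combined conduct and hyperactivity scale scores (0-20) (Survey"). SAP Table 6 gives the baseline mean (SD) on that combined scale as 7.46 (4.25) in 6,179 control pupils and 7.62 (4.37) in 7,214 intervention pupils. The SAP does not set these SDs against 1.74.

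**The concern.** An SD of 1.74 and an SD of about 4.3 cannot both describe the same score. The SAP replaced the planning ICC of 0.03 with the observed 0.015 in Table 4 but left the planning SD in place. If the observed SD is right, the only statement of the target in points describes an effect about 2.5 times smaller than 0.2 SD. SAP 2.3.11 standardises the result by the empty-model SD. If that is close to the baseline SD, a true 0.34-point effect would be reported as about 0.08, while a reader relying on the planning text would expect 0.2.

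The second matter is traceability. If 527 belongs to a different power level from the one printed, then the total of 6,798 and the whole chain of QED sample sizes carry the wrong label.

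**Working it through.** **Inputs.** Planning SD 1.74, target 6.0 versus 5.66 and 527 per group (SAP 2.2); power 0.8 and two-sided alpha 0.05 (SAP Table 4, SAP 3.2); baseline SDs and numbers (SAP Table 6); 100 schools × 160 pupils at ICC 0.03, and 78 schools × 166 at ICC 0.015 (SAP Table 4); design effect 5.8 (SAP 2.2).

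**1. The plan's translation into points.** 0.2 × 1.74 = 0.348, printed as 0.34. So the target follows from an SD of 1.74, apart from rounding (0.34/1.74 = 0.195).

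**2. The same translation with the observed SD.** Pooled SD = √[(6,178 × 4.25² + 7,213 × 4.37²)/13,391] = 4.315, and 4.315/1.74 = 2.48.

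- 0.34/4.315 = 0.079 SD
- 0.2 × 4.315 = 0.86 points
- planned MDES: 0.1064 × 4.315 = 0.46 points
- achieved MDES: 0.094 × 4.315 = 0.41 points

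Both MDES values, in points, are larger than the 0.34-point target.

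**3. Power for a true 0.34-point difference.** In SD units, SE = √[ICC/(P(1−P)J) + (1−ICC)/(P(1−P)Jm)], where J is schools, m is pupils per school and P is the fraction of schools in the intervention arm. The t distribution has J−2 degrees of freedom.

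- 78 × 166, ICC 0.015, P = 40/78: SE = 0.0328; 0.0788/0.0328 = 2.40; power about 66%.
- 100 × 160, ICC 0.03, P = 0.5: SE = 0.0380; 0.0788/0.0380 = 2.07; power about 54%.

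As a check on the formula, 2.80 × 0.0380 = 0.1064, which reproduces the planned MDES at 80% power. For 78 schools it gives 0.093 against the printed 0.094, which is immaterial here.

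These powers assume zero pre-post correlation, as the SAP does. The primary model adjusts for baseline. The documents give no correlation, so the range below is an assumption: 78 × 166, with the same correlation r at pupil and school level, so that both variance terms are multiplied by 1−r².

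| r | Power for 0.34 points |
|---|---|
| 0 | 66% |
| 0.5 | 78% |
| 0.6 | 84% |
| 0.7 | 91% |

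If only the pupil-level variance falls, r = 0.6 gives 71%. Power for 0.2 SD exceeds 99% in both designs even at r = 0.

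**4. The 527.** Two-sample t-test, two-sided alpha 0.05, effect size 0.2:

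- 80% power: 393.4, so 394 per group
- 90% power: 526.3, so 527 per group

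Power at 527 per group is 90.0%. Using the rounded 0.34/1.74 does not recover 527: it needs 413 at 80% and about 551 at 90%. One-sided tests do not recover it either (310 at 80%, 429 at 90%).

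**5. What follows from 527.** Main trial: 2 × 527 = 1,054; 1,054/0.9 = 1,171.1, printed as 1,172; 1,172 × 5.8 = 6,798. QED with 15 pupils per school: 527 × 1.45 = 764 per group; 2 × 764 = 1,528; 764 × 0.7 = 535; 2 × 535 = 1,070. All of these reproduce the plan.

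At 80% power: 2 × 394 = 788; 788/0.9 = 875.6, so 876; 876 × 5.8 = 5,081. QED: 394 × 1.45 = 571 per group, about 1,143 in total, and about 800 after the 30% reduction.

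**The case against.** The strongest reply is that nothing in the analysis depends on 1.74 or on 0.34. The funder's criterion is a standardised MDES below 0.20, Tables 3 and 4 are in SD units, and the result will be reported in SD units. The declared target is an effect size of 0.2; the points are only its translation. All of that stands, and it is why this is a correction to the text and not a flaw in the design.

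It is also fair that the observed SD came after the protocol, so the protocol's planning value was not wrong against data then in hand. But the SAP prints the baseline SDs and still repeats 1.74.

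Three stronger readings are tempting and are not supported:

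- A reader might infer that the trial is underpowered. For 0.2 SD it is not, and labelling a 90% sample size as 80% asks for about a third more pupils than needed (527/394 = 1.34), which is conservative.
- A reader might infer that 0.34 points is out of reach at 80% power. That holds with zero correlation, which the SAP itself calls the most conservative case. With baseline adjustment 80% may or may not be reached, and the documents cannot settle it.
- A reader might infer that the 50-school minimum rests on 527. The step is not shown: 6,798/160 = 42.5 schools, and the SAP describes 25 per arm as what an efficient cluster trial needs.

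**Conclusion.** Both figures are wrong as written and should be fixed.

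First, the raw-score target is inconsistent with the SAP's own data by a factor of about 2.5. This rests on Table 6 being on the same combined 0-20 scale as the planning values, which is how the SAP labels it. The norms source and the footnote's standardised SD cannot be checked from the documents, but no derivation is offered that would reconcile the two SDs.

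Second, 527 per group matches 0.2 SD at 90% power with two-sided alpha 0.05, while the MDES of 0.1064 matches 80%. The SAP therefore uses two power levels under one label.

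The consequence is limited to how the plan and its results will be read. The standardised MDES values and the adequacy of the sample for 0.2 SD are unaffected.

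**What to change.** In SAP 2.2, add a dated note giving the observed pooled SD of 4.32 beside the planning value of 1.74, as Table 4 already does for the ICC. Restate the target in points: 0.2 SD is about 0.86 points, and the achieved MDES of 0.094 is about 0.41 points. Explain the derivation of 1.74, or say that it is superseded.

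Then choose one of two courses for the sample-size chain:

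- label 527 / 1,054 / 1,172 / 6,798 as 90%-power figures; or
- restate them at 80%, keeping the plan's own design effect of 5.8, as 394 / 788 / 876 / about 5,081.

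Apply the same choice to the QED: the 80% statement, 1,528 and 1,070 in SAP 3.2 and Protocol Appendix 2, and the rows of SAP Table 7 and Protocol Appendix Table 3 that follow from the base sample (adjusted sample, sample after weighting, number of intervention schools). The design-effect row does not change. Protocol 3.5 needs only a cross-reference to the SAP note and the same power label.

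The cost is wording and a few table cells, with no change in enrolment or analysis. It should be done before outcome data are seen, so that the raw-score benchmark is fixed in advance.
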